7.6 Secondary Efficacy Endpoint measures

In order to assess the correlation of MBT with other measures of liver disease the following endpoint measures will be collected:

| | |
|---|---|
| Exalenz Bioscience Ltd. | Last update: February 20, 2018 |
| Study Title: Companion protocol for the ¹³C-Methacetin Breath Test (MBT) for use in Bristol-Myers Squibb phase 2b studies for BMS-986036 (PEG-FGF21), under Protocols MB130-068 and MB130-069 | Protocol: BMS-EX-0118 Version: 1.0 |
| Document No: CSP000002 | Page 22 of 38 |

For all study cohorts: MBT results for each MBT visit (day 1, week 24, week 48,) as well as changes in MBT results (CPDR30/PDR peak or other breath test parameters).

The other measures of liver disease that will be collected in this study are as follows:

Liver Fibrosis stage and NAS as determined by Liver Biopsy, PDFF as determined by MRI where available, Liver Stiffness as determined by MRE where available, Serum Biomarker Pro-C3

Additional measures for cohort 2: MELD and CTP scores, Liver Stiffness as determined by Fibroscan® Elastography, Liver-related Clinical Outcome defined as the first occurrence of any one of the following: all-cause mortality, MELD score ≥ 15 , liver transplant, hepatocellular carcinoma (HCC), ascites requiring medical intervention, hospitalization (≥ 24 hours) for onset of variceal bleed, hepatic encephalopathy, spontaneous bacterial peritonitis.

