3 STUDY OBJECTIVES AND ENDPOINTS

3.1 *Study Objectives*

3.1.1 *Primary Objective*

The data generated in this companion study will be used to demonstrate the ability of the MBT to evaluate patient response to treatment with BMS-986036, comparing placebo to each treatment arm individually. Primary efficacy assessment will be performed using the Week 24 and the Week 48 visit measures compared to Day 1 (change from baseline) for the combined population of the two cohorts, according to availability, by dose of the BMS drug under study.

The same assessments for each study cohort independently will be reported.

3.1.2 *Secondary Objective*

The following assessments will be done by treatment arm by dose of the BMS drug under clinical investigation and combined arms on the combined population of the two study cohorts:

1. To demonstrate the short and long-term prognostic value (3 months, 6 months and 1 year, respectively) of MBT for liver disease deterioration (reported as liver-related

Meridian Bioscience Israel Ltd.	Last update: May 05, 2021
SAP for Protocol BMS-EX-0118: Companion protocol for the ¹³C-Methacetin Breath Test (MBT) for use in Bristol-Myers Squibb phase 2b studies for BMS-986036 (PEG-FGF21), under Protocols MB130-068 and MB130-069	Document Version: 1.0
Document Nº: CSD00114	Page 9 of 21

clinical outcome events). Assessment will be performed using MBT from the Day 1, Week 24 and Week 48 visits.

2. To assess the ability of changes in the MBT to reflect biopsy proven changes in fibrosis and/or NAS as assessed by a central reader, where available, at Week 24 (or at least Week 20 in cases of an Early Termination time point) (for cohort 1) or at Week 48 (for cohort 2) compared to the baseline biopsy from the screening visit.
3. To assess the ability of changes in the MBT to reflect changes in liver stiffness as measured by Magnetic Resonance Elastography (MRE), where available, at Week 24 and Week 48 (or at Early Termination) compared to baseline MRE from the screening visit.
4. To assess the ability of changes in the MBT to reflect changes in Proton Density Fat Fraction (PDFF) as measured by Magnetic Resonance Imaging (MRI), where available, at Week 24 and Week 48 (or Early Termination), compared to baseline MRI from the screening visit.

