5. To assess the ability of changes in the MBT to reflect changes in Serum Pro-C3, where available, at Week 24 and Week 48 of treatment (or Early Termination), compared to baseline Pro-C3 from the screening visit.

The same assessments for each study cohort independently will be reported.

The following additional objectives are applicable for cohort 2 only:

1. To assess the ability of changes in the MBT to reflect changes in liver stiffness as measured by “Fibroscan” elastography, where available, at the Week 48 visit (or earlier if there was an Early Termination) compared to the screening visit.
2. To assess the ability of changes in the MBT to reflect changes in the Model for End-stage Liver Disease (MELD) score, where available, at Week 24 and Week 48 visits compared to study Day 1.
3. To assess the ability of changes in the MBT to reflect changes in the Child-Turcotte-Pugh Scoring (CTP) score, where available, at Week 24 and Week 48 (or Early Termination) compared to study Day 1.

Meridian Bioscience Israel Ltd.	Last update: May 05, 2021 Document Version: 1.0
SAP for Protocol BMS-EX-0118: Companion protocol for the ¹³C-Methacetin Breath Test (MBT) for use in Bristol-Myers Squibb phase 2b studies for BMS-986036 (PEG-FGF21), under Protocols MB130-068 and MB130-069	
Document Nº: CSD00114	Page 10 of 21

3.1.3 *Exploratory Objective*

- To assess the ability of the MBT to monitor patient status in comparison to other available measures, such as Liver Fibrosis stage, NAS, MELD, CTP, PDFF, Liver Stiffness, Serum Biomarker or Pro-C3.

3.1.4 *Safety Objective*

Evaluation of safety related to the MBT.

3.2 *Study Endpoints*

3.2.1 *Primary Endpoint*

The MBT's ability to measure the effect of BMS-986036 treatment on the metabolic capacity of the liver at Week 24 and Week 48 visits during the Double-Blind Treatment Period, as compared to changes in placebo treated subjects.

3.2.2 *Secondary Endpoints*

In order to assess the correlation of changes in MBT with changes in other measures of liver disease, the following endpoint measures will be collected, where available:

For all study cohorts: MBT results for each MBT visit (Day 1, Week 24, Week 48, or Early Termination visits) as well as changes in MBT results (cPDR₃₀, PDR_{peak} or other breath test parameters).

The other measures of liver disease that will also be collected in this study are as follows:

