4 STUDY DESIGN

Please refer to BMS' protocols MB130-068 and MB130-069 - IND 125297.

This study is a feasibility companion protocol that will rely on the data generated by BMS's studies of BMS-986036 (PEG-FGF21) under protocols MB130-068 and MB130-069 (IND 125297), which are defined in this companion protocol as two separate study cohorts (1 and 2, respectively) with the exception of the MBT, for which Exalenz may extract additional data based on the recorded MBT results. The MB130-068 and MB130-069 studies are Phase 2b, multicenter, double-blind, randomized, placebo-controlled, parallel-group studies to demonstrate the safety and efficacy of BMS-986036 in the treatment of subjects with NASH and stage 3 liver fibrosis or compensated cirrhosis with up to 48 weeks of treatment. The study is feasibility for drug response monitoring however the data may be used by Exalenz for future submissions.

As described in the BMS protocols, subjects will be enrolled and randomized via interactive response technology (IRT) to receive BMS-9860936 10mg QW, BMS-986036 20mg QW, BMS-9860936 40mg QW or matching placebo QW in a 1:1:1:1 ratio.

The BMS studies' treatment durations will each consist of two periods:

1. A 48-week, Double-Blind Treatment Period, during which the subjects will receive blinded study medication (BMS-986036 10mg, 20 mg, 40mg QW or matching placebo QW). During the Double-Blind Treatment Period, subjects will be evaluated for safety and efficacy every 4 weeks (± 5 days) through Week 24 and every 8 weeks (± 5 days) from Week 24 through Week 48.
2. A Follow up period, during which subjects will be evaluated for safety and efficacy for 4 weeks through Week 52.

Meridian Bioscience Israel Ltd.	Last update: May 05, 2021
SAP for Protocol BMS-EX-0118: Companion protocol for the ¹³C-Methacetin Breath Test (MBT) for use in Bristol-Myers Squibb phase 2b studies for BMS-986036 (PEG-FGF21), under Protocols MB130-068 and MB130-069	Document Version: 1.0
Document Nº: CSD00114	Page 12 of 21

3. A Follow up period of at least 6 months and up to 14 months after the Week 52/ PTFU Visit for the collection of additional DXA assessment (in all participants) and immunogenicity assessments (in participants for whom Long-Term Immunogenicity Follow-Up Visits are required.) Any liver related complication event will be recorded.

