In order to show the ability of the MBT to measure the effect of BMS-986036 treatment on the metabolic capacity of the liver after Week 24 and Week 48 visits, as compared to changes in placebo treated subjects, the primary endpoint will be analyzed using a responder analysis, where any increase of MBT value will be considered as a response while a same value or a decrease of the MBT value will be considered as non-response.

The primary analysis will be conducted on the mEA set, with the PDR_{peak} and cPDR₃₀ responder rate of Week 24 and Week 48 of data from both BMS' studies.

Individual analyses for each cohort separately will also be reported.

8.4.2 *Secondary Endpoints*

8.4.2.1 *Prognostic Value of MBT in Overall Event-Free Survival*

In order to assess the prognostic value of MBT in prediction of liver disease deterioration (reported as liver-related clinical outcome events), the endpoint measures will be point estimates of Cox Regression's Hazard Ratio for classifying Subjects into risk groups for clinical deterioration with respective exact two-sided 95% confidence intervals in the placebo and treatment arms as determined by MBT. The MBT parameter to be used to predict liver-related clinical outcome events is PDR_{peak}. Any PDR_{peak} value of less or equal to 20 %/h (see **Appendix A** for detailed description of parameter calculation) will be considered as 'high risk' and any value above that threshold will be considered as 'lesser risk' (additional cut-off values may be explored). The dichotomic MBT result will be tested for significance using the Cox proportional hazards regression model with site and randomized arm as covariates. If the randomized arm factor is found non-significant (i.e. p-value > 0.05), then this factor will not be a covariate for the main analysis to be performed. If the randomized arm factor is found statistically significant (i.e. p-value ≤ 0.05), then the main analysis will be performed keeping this factor as a covariate (to 'adjust' the analysis for treatment).

The time-to-first event will be derived as the number of days between the Day 1 MBT test and the date when the first event occurs or when a subject is censored (i.e., event/censored date minus

Meridian Bioscience Israel Ltd.	Last update: May 05, 2021

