SAP for Protocol BMS-EX-0118: Companion protocol for the ¹³C-Methacetin Breath Test (MBT) for use in Bristol-Myers Squibb phase 2b studies for BMS-986036 (PEG-FGF21), under Protocols MB130-068 and MB130-069	Document Version: 1.0
Document Nº: CSD00114	Page 17 of 21

Day 1 MBT date plus 1). Subjects will be censored at their last study visit for the following reasons:

- If a subject discontinues the study prior to the end of the study without experiencing an event
- If a subject reaches the Final Treatment visit without experiencing an event

Survival analysis will be conducted using the Cox proportional hazard model. The model summary will include the number of subjects in the model, and a table with each covariate in a separate line specifying the coefficient's value, Hazard Ratio, Hazard Ratio 95% Confidence Interval and p-value. In addition, a Kaplan-Meier plot for event-free survival will be presented, stratified by MBT parameter along with the MBT parameter log-rank p-value. Additionally, a crosstab table of MBT parameter and events will be presented.

8.4.2.2 Correlations between changes in MBT parameters and changes in other liver related parameters

Repeat MBT results (cPDR₃₀, PDR_{peak} or other breath test parameters) and their changes in subjects with and without treatment (BMS-986036) for nonalcoholic steatohepatitis (NASH) at Day 1, Week 24 and Week 48 (or Early Termination visits) will be compared and tested for correlation to baseline, as well as repeat results (change from baseline), for the following measurements:

- a. Biopsy based Fibrosis and/or NAS score
- b. Liver stiffness as measured by MRE
- c. PDFF as measured by MRI
- d. Serum Pro-C3 results
- e. Liver elastography by Fibroscan (in cohort 2 only)
- f. MELD scores (in cohort 2 only)
- g. CTP scores (in cohort 2 only)

Linear Regression will be applied in order to test for significance of the correlations between MBT and the liver measurements listed above.

Changes in MBT are measured as the difference between baseline and each of the MBT visits as well as the change in measurements between two subsequent visits in each of the two treatment groups.

Meridian Bioscience Israel Ltd.	Last update: May 05, 2021
SAP for Protocol BMS-EX-0118: Companion protocol for the ¹³C-Methacetin Breath Test (MBT) for use in Bristol-Myers Squibb phase 2b studies for BMS-986036 (PEG-FGF21), under Protocols MB130-068 and MB130-069	Document Version: 1.0
Document Nº: CSD00114	Page 18 of 21

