8.5 Site Poolability

Primary efficacy analysis will be reported for each cohort separately as well as for each site/group of sites (see next section) separately.

For sites with less than 10 subjects, the following pooling of sites method will be applied for each cohort separately: Sites will be sorted from smallest to largest based on the number of randomized subjects with valid baseline MBT results. The smallest site will be pooled with the second smallest, and if necessary with the next sites in line until the site group reaches 10 subjects or more. The site value for those sites will be assigned "Site Group 1". Then the next site in line, if lower than 10 subjects, will be pooled with the sites after it until the site group reaches at least 10, and so forth until all sites or site groups have at least 10 subjects. Furthermore, site by MBT dichotomy interaction will be added to the Linear and Cox regression models as a covariate to test for site effect on the exploratory endpoints.

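### The pooled prognostic log-rank test, Kaplan-Meier plot and crosstab have no cohort stratum, so they cannot separate MBT from cohort; the Cox hazard ratio is protected if site-group levels stay distinct by cohort

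*SAP*

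**What the plan says.** SAP 3.1.2 sets the secondary objectives, including prognosis, by treatment arm and for "combined arms on the combined population of the two study cohorts". It then adds: "The same assessments for each study cohort independently will be reported".

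SAP 8.4.2.1 names the Cox hazard ratio as the endpoint measure. MBT enters as one dichotomy (PDRpeak at or below 20 %/h against above) in a "Cox proportional hazards regression model with site and randomized arm as covariates". Two further outputs follow: "a Kaplan-Meier plot for event-free survival will be presented, stratified by MBT parameter along with the MBT parameter log-rank p-value", and "a crosstab table of MBT parameter and events will be presented". Cohort appears in none of these.

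SAP 8.5 groups sites with fewer than 10 subjects: "the following pooling of sites method will be applied for each cohort separately". The first group is labelled Site Group 1, and no cohort prefix is stated.

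On event capture the documents are mixed.
- Protocol 7.6 places the composite clinical outcome in the block that begins "Additional measures for cohort 2: MELD and CTP scores". Protocol 7.7, 7.7.2 and 7.7.7 likewise specify visit-by-visit outcome evaluation and MELD scoring for cohort 2.
- Protocol 3.2 says that all liver-related outcome events will be captured, naming no cohort but pointing to 7.7.2.
- SAP section 4, describing both parent studies, says: "Any liver related complication event will be recorded".
- SAP 3.2.2 lists the composite outside its cohort 2 block, and SAP section 2 says that the SAP prevails over the protocol.

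**The concern.** The two cohorts are separately randomised studies defined by disease stage. Cohort is plausibly related to both sides of the comparison.

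- **MBT group.** Protocol 3.2 links advanced liver disease to low MBT values, although it does not compare stage 3 fibrosis with compensated cirrhosis. One cut-off serves both cohorts.
- **Recorded events.** The composite is largely made up of complications of cirrhosis, so a higher risk in cohort 2 is plausible. MELD of 15 or more is itself an event component, and MELD scoring is specified only for cohort 2.

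If low MBT is commoner in cohort 2 and events are more often recorded there, a pooled display split by MBT alone will show low MBT as adverse even when MBT carries no information within either cohort. The per-cohort results would not show this pattern, but they do not correct the pooled p-value printed beside them. The SAP also leaves open using the data in future submissions.

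**Working it through.** The documents give no event rate, hazard ratio, low-MBT share or cohort split for tested subjects, so there is no planned figure to reproduce. What follows illustrates size under stated assumptions, with no MBT effect inside either cohort.

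**Inputs from the documents.** Parent study sizes are 160 and 100, and fewer than 80 subjects are expected with valid baseline and post-treatment MBT (SAP sections 2 and 4.1). Splitting 80 in the ratio 160:100 gives N1 = 49 and N2 = 31.

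**Assumed inputs.** Event risk r2 = 15% in cohort 2 and r1 = 3% or 6% in cohort 1. Low-MBT shares (p1, p2) are as tabulated.

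**Step 1: crude pooled risk ratio.**

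Risk in low MBT = (N1·p1·r1 + N2·p2·r2) / (N1·p1 + N2·p2). Risk in the rest replaces p with 1 − p.

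Worked case, p1 = 15%, p2 = 50%, r1 = 3%:
- low MBT: (7.35 × 0.03 + 15.5 × 0.15) / 22.85 = 2.5455 / 22.85 = 11.1%
- rest: (41.65 × 0.03 + 15.5 × 0.15) / 57.15 = 3.5745 / 57.15 = 6.25%
- ratio = 1.78, where the within-cohort ratio is 1.

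**Step 2: log-rank test.** The setting was 5,000 simulated studies with exponential event times and one year of follow-up. The count is of studies with two-sided p<0.05 and low MBT worse.

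| Low-MBT share, cohort 1 / cohort 2 | Crude ratio, r1 = 3% / 6% | Pooled log-rank, r1 = 3% / 6% | Stratified by cohort, r1 = 3% / 6% |
|---|---|---|---|
| 5% / 40% | 2.03 / 1.58 | 18.7% / 12.6% | 2.9% / 3.3% |
| 15% / 50% | 1.78 / 1.43 | 14.4% / 10.1% | 2.4% / 2.8% |
| 30% / 60% | 1.57 / 1.31 | 8.9% / 6.5% | 2.0% / 2.6% |
| 30% / 40% | 1.18 / 1.10 | 5.7% / 4.9% | 3.3% / 3.3% |
| 30% / 30% | 1.00 / 1.00 | 3.5% / 3.6% | 3.3% / 3.7% |

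Repeat runs move these rates by about one percentage point, hence about 4-20% pooled and 2-3.5% stratified where the shares differ. Expected events are 49 × 0.03 + 31 × 0.15 = 6.1 and 49 × 0.06 + 31 × 0.15 = 7.6, so any single estimate is very imprecise.

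**Step 3: lower event risk.** With r2 = 5% and r1 = 1% or 2%, the crude ratios are unchanged, because they depend only on r2/r1. Expected events fall to 49 × 0.01 + 31 × 0.05 = 2.0 and 49 × 0.02 + 31 × 0.05 = 2.5. The pooled rate is about 3-14%, with little or no excess in some cases.

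**Step 4: the Cox model.** If site-group levels are distinct by cohort, their indicators add up to the cohort indicator, so the model adjusts for cohort without naming it. A large-sample check (60,000 subjects; r1 = 2%, r2 = 15%; low-MBT shares 10/30%, 10/50% and 20/60%; true hazard ratio 1) gave these hazard ratios for low MBT:
- distinct site groups: 0.97-1.00
- group labels reused across cohorts: 1.54-2.05
- sites serving both studies under one code: 1.64-2.25

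This check omits the arm term and the site-by-MBT interaction of SAP 8.5, so it shows the mechanism and not the planned model.

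**The case against.** **The criticised outputs are supplementary.** SAP 8.4.2.1 makes the Cox hazard ratio the endpoint measure. The log-rank test, plot and crosstab are additions, all p-values are nominal, and unconfounded per-cohort results are planned. This stands, and it keeps the point minor. A reader might infer from the Cox covariate list that the hazard ratio itself is confounded by cohort. The documents do not support that, because SAP 8.5 builds site groups within each cohort. The exposure is conditional: SAP 8.4.2.1 says only site, and the SAP does not say that labels or site codes are kept apart.

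**Marginal prognosis is a legitimate question.** If subjects with cirrhosis truly have lower MBT and more events, low MBT does predict events in the mixed population. The excess rejections in step 2 are then not simply false positives. This also stands. Only differential ascertainment is bias in the strict sense. The remainder is an association unadjusted for stage, which should be labelled as such.

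**Cohort 1 ascertainment is unknown.** A reader might infer that events are not captured in cohort 1 at all. Protocol 3.2 and SAP section 4 point the other way, and actual capture rests on parent protocols not available here. Ascertainment is uncertain, not absent.

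**The inputs are assumed.** They are, and step 3 shows that the excess can disappear when events are rarer.

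**Conclusion.** The omission is real and its effect is minor. The pooled log-rank p-value, Kaplan-Meier plot and crosstab mix MBT with cohort. The Cox hazard ratio does not, provided site levels are distinct by cohort. Under the assumptions above, the crude pooled ratio is about 1.1-2.0 where the within-cohort ratio is 1. The chance of a nominally significant pooled log-rank result against low MBT is about 4-20%, against about 2-3.5% stratified. At 5% cohort 2 risk it is about 3-14%, and it is close to its usual level when the cohorts have similar low-MBT shares.

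Larger figures arise if cohort 1 is given no events: the crude ratio runs from 1.3 to 2.9. They should not be carried as the expected size. They apply only if cohort 1 truly has no events or unassessed subjects are counted as event-free. If such subjects are excluded as missing under SAP 5.1, the pooled set reduces to cohort 2 and there is no cohort confounding. The SAP does not say which of these it intends.

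**What to change.** 1. In SAP 8.4.2.1, stratify the pooled log-rank test and the pooled Cox model by cohort.
2. In SAP 8.5, state that site and site-group levels are distinct by cohort, including for any site active in both studies.
3. Show the Kaplan-Meier plot and crosstab by cohort. Label any unstratified pooled display as a marginal association not adjusted for disease stage.
4. State which outcome components are ascertained in cohort 1, and whether cohort 1 subjects without scheduled outcome evaluation are treated as missing or as event-free.

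The cost is SAP wording. SAP section 2 allows amendments until Exalenz independently accesses the data. The statistical price is slightly less precision. A cohort with no events also contributes nothing to the stratified estimate, which would then equal the other cohort's result. This is a cheap improvement.

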8 STATISTICAL ANALYSES

8.1 *General Considerations for Data Analyses*

All analyses will be performed using either SAS® v9.4 or higher (SAS Institute, Cary NC, US) or the R software version 4.0.3 or higher (R Development Core Team. Vienna, Austria).

The standard summary statistics for continuous variables are: N, mean, standard deviation, median, minimum and maximum. The standard summary statistics for categorical variables are: count and proportion.

The analyses will be descriptive by nature, nominal p-values will be reported for supplementary information. Any statistical tests performed, will be two-sided. The significance level of findings will be equal to or lower than 5%. Where confidence limits are appropriate, the confidence level will be 95%. Nominal p-values and unadjusted confidence intervals will be presented.

8.2 *Baseline Definitions*

The study baseline will be defined as the Day 1 visit value, unless specifically mentioned otherwise. In case of repeat measurements, the latest value associated with the Day 1 visit will be considered the baseline value.

For survival models: The baseline MBT test will be defined as the baseline and day 0 of follow up.

8.3 *Disposition of Patients*

Subject dispositions will be summarized based on all subjects screened into the study separated by study cohort (and combined), and for each treatment group.

The following subject disposition information will be presented:

- The number and percentage of subjects who had valid MBT for each visit.
- The number and percentage of reasons for not having a valid MBT for each visit.
- The number and percentages of subjects that were excluded from the EA and mEA analysis sets, by reason for exclusion.

Meridian Bioscience Israel Ltd.	Last update: May 05, 2021
SAP for Protocol BMS-EX-0118: Companion protocol for the ¹³C-Methacetin Breath Test (MBT) for use in Bristol-Myers Squibb phase 2b studies for BMS-986036 (PEG-FGF21), under Protocols MB130-068 and MB130-069	Document Version: 1.0
Document Nº: CSD00114	Page 16 of 21

8.4 *Efficacy Analyses*

8.4.1 *Primary Endpoint*

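### SAP objective 1 promises prognosis at three horizons from three breath tests, but section 8.4.2.1 gives one clock from Day 1, no horizon estimate and an ambiguous censoring visit

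*SAP*

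**What the plan says.** SAP 3.1.2, secondary objective 1, is to show the "short and long-term prognostic value (3 months, 6 months and 1 year, respectively) of MBT for liver disease deterioration". It adds: "Assessment will be performed using MBT from the Day 1, Week 24 and Week 48 visits".

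For survival models, SAP 8.2 states: "The baseline MBT test will be defined as the baseline and day 0 of follow up". SAP 8.4.2.1 then defines one time variable, which "will be derived as the number of days between the Day 1 MBT test and the date when the first event occurs" or the subject is censored. The predictor is PDRpeak, split at 20 %/h. The outputs are a Cox hazard ratio, a crosstab of MBT group by events, and "a Kaplan-Meier plot for event-free survival will be presented, stratified by MBT parameter along with the MBT parameter log-rank p-value".

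On censoring, 8.4.2.1 says "Subjects will be censored at their last study visit for the following reasons". The two reasons are discontinuing without an event, and this: "If a subject reaches the Final Treatment visit without experiencing an event". SAP section 4 puts the last dose at Week 48, a post-treatment visit at Week 52, and a further follow-up of 6 to 14 months in which liver-related complications are still recorded. Protocol section 5 also collects these events in that period, and protocol 7.7 does so for cohort 2.

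**The concern.** The objective and the analysis stand in the same document and do not match. The rule in SAP section 2 that the SAP overrides the protocol therefore cannot settle the difference. Followed exactly, the plan leaves unanswered whether a Week 24 or Week 48 MBT predicts later liver events. It also gives no separate answer for short-term and long-term prognosis: one hazard ratio under proportional hazards averages over all follow-up.

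Two competent analysts could also choose different censoring visits and so count different events. SAP section 4 says that the data may support future submissions, so even a descriptive prognostic result needs a defined predictor, clock and end of follow-up.

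**Working it through.** The plan gives no event rate, event count or horizon-specific figure for this analysis, so there is nothing to reproduce. The check sets the texts side by side and then counts days.

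**Objective against analysis**

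| Element | SAP 3.1.2, objective 1 | SAP 8.2 and 8.4.2.1 |
|---|---|---|
| MBT used as predictor | Day 1, Week 24, Week 48 | Visit not stated; Day 1 follows from the baseline definition and the clock |
| Time origin | Not stated | Day 1 MBT only |
| Horizons | 3 months, 6 months, 1 year | None named |
| Estimate | Short- and long-term prognostic value | Overall hazard ratio, Kaplan-Meier plot, untimed crosstab |

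The Week 24 and Week 48 tests reappear in SAP 8.4.2.2, but only for correlation with other liver measures. For this same analysis, protocol 9.2.2 asked for estimates at 48 weeks or more. The SAP does not carry that over.

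**Follow-up after each test**

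Inputs: Week 24 = 24 × 7 = 168 days; Week 48 = 48 × 7 = 336; Week 52 = 52 × 7 = 364. Assumptions: visits are on schedule and a month is 365.25/12 = 30.44 days.

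- Week 52 + 6 months = 364 + 182.6 = 547 days.
- Week 52 + 14 months = 364 + 426.1 = 790 days.
- Follow-up = censoring day − MBT day.

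| Censoring visit | From Day 1 MBT | From Week 24 MBT | From Week 48 MBT |
|---|---|---|---|
| Week 48 | 336 | 168 | 0 |
| Week 52 | 364 | 196 | 28 |
| Week 52 + 6 months | 547 | 379 | 211 |
| Week 52 + 14 months | 790 | 622 | 454 |

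The horizons are 3 × 30.44 = 91 days, 6 × 30.44 = 183 days, and 1 year.

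- *Week 48 or Week 52 censoring.* The Week 48 MBT has at most 28 days after it, against 91 for the shortest horizon. No pairing of visits with horizons changes this.
- *Long-term follow-up.* The Week 48 MBT has 211 to 454 days, which covers 3 and 6 months. One year of 365.25 days needs (336 + 365.25 − 364) / 30.44 = 11.1 months after Week 52, so it is covered only for subjects followed that long.
- *Meaning of 1 year.* SAP 4.1 describes up to three tests over 1 year, although the scheduled span is 336 days. If the horizon means 48 weeks, a Day 1 clock stopped at Week 48 just reaches it. If it means 365 days, that clock falls 365 − 336 = 29 days short.

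**The case against.** **The SAP does state a censoring rule.** A reader might infer that the censoring date is undefined. That goes too far: 8.4.2.1 censors at the last study visit. What is missing is the link from that term, and from the Final Treatment visit, to a study week. The date is ambiguous, not absent.

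**The harm depends on the reading.** Because the last dose is at Week 48, a reader might conclude that follow-up stops there, so that the Week 48 test can predict nothing and later events are discarded. The documents do not support this as fact. Grammatically, the Final Treatment visit is a reason for censoring, while the last study visit sets the date. The section's title, on overall event-free survival, and the recording of events in long-term follow-up both fit a later date. This objection stands: the lost follow-up is conditional.

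**Use of Day 1 alone is an inference.** The SAP never says that the dichotomised value is the Day 1 PDRpeak. The inference is strong, but the silence is itself a gap. A Week 24 or Week 48 value placed on a Day 1 clock would credit the time a subject had to remain event-free before being tested.

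**The study is descriptive and small.** SAP sections 2 and 6.1 rule out formal testing, and fewer than 80 subjects are expected to have valid baseline and post-treatment MBT results. Section 2 also lets additional analyses be documented in the study report. This limits the severity. It does not close the gap, because analyses and censoring dates chosen after the data are seen are weaker than ones set beforehand.

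**The Kaplan-Meier plot can be read at 3 and 6 months.** It can, from Day 1. But no estimate with an interval is specified there, and the plot says nothing about the later tests.

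**Conclusion.** The mismatch is real. Objective 1 names three tests and three horizons; 8.4.2.1 supplies one time origin, no estimate at a named horizon, and no analysis of the Week 24 or Week 48 MBT against later events. The visit supplying the predictor and the visit ending follow-up both need stating.

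The censoring visit for an event-free completer spans day 336 to about day 790. Censoring at Week 48 or Week 52 leaves the Week 48 MBT with 0 or 28 days, so its part of the objective could not be met at any horizon, and events recorded later would go unused. Censoring at the end of long-term follow-up removes both harms. In either case the later tests still have no prognostic analysis and no horizon estimate is specified.

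The figures assume on-schedule visits and average month length. The number of events affected cannot be sized, because the documents give no event rate. This is a cheap improvement to a descriptive plan; it does not invalidate the Day 1 analysis.

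**What to change.** Amend SAP 8.4.2.1 before data access, as SAP section 2 allows:

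1. State that the Day 1 analysis uses the Day 1 PDRpeak. Add descriptive landmark analyses with time zero at the Week 24 MBT and at the Week 48 MBT, each in subjects event-free at that date. Do not enter a later MBT as a fixed covariate on the Day 1 clock.
2. By MBT risk group, report event-free proportions with 95% confidence intervals and numbers at risk at 3, 6 and 12 months where follow-up allows, and event counts otherwise. Define 1 year as 48 weeks or 365 days.
3. Name one censoring date. Either window, on treatment or including recorded follow-up events, can be the main one; report the other as a sensitivity analysis. If no follow-up after Week 48 will be used, remove the Week 48 MBT from objective 1.

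The cost is SAP wording and a little programming. The downsides should be stated: estimates will be sparse and only descriptive, time after Week 48 is off drug, and long-term follow-up may be incomplete for some subjects.
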